demographics, background, and baseline characteristics and also to efficacy data analyses, including the primary endpoint analysis. In addition, *period baseline* is defined as the most recent non-missing measurement (scheduled or unscheduled) collected before the first dose of study drug in each Treatment Period. For Treatment Period 2, the baseline should be from an assessment measured after the TE period for Treatment Period 1. This definition will be applied to all safety data analysis. For ECG, baseline for Period 1 will be defined as the average of the 3 pretreatment measurements on Day 1. For sweat chloride, the study baseline value will be the mean of assessment values on the left and the right arm at the most recent time point prior to the first dose of study drug in the study. If the result from only one of the arms is available then the result from that arm will be considered as baseline.

**Change (Absolute change) from study baseline** will be calculated as post-baseline value – study baseline value.

**Relative change from study baseline** will be calculated as  $100 \times (\text{post-baseline value} - \text{study baseline value}) / \text{study baseline value}$ .

**Change (Absolute change) from period baseline** will be calculated as post-baseline value – period baseline value.

**Relative change from period baseline** will be calculated as  $100 \times (\text{post-baseline value} - \text{period baseline value}) / \text{period baseline value}$ .

**Unscheduled Visits:** Unscheduled visit measurements will be included in the following:

- (1) derivations of measurements at scheduled visits per specified visit windowing rules below;
- (2) derivations of baseline/last on-treatment measurements;
- (3) derivations of the maximum/minimum on-treatment values and maximum/minimum changes from baseline values for safety analyses;
- (4) data listings where appropriate.

**Visit Windowing Rules:** Section 10.2 defines the windows for protocol-defined visits. The windows will be applied using the following rules for both scheduled and unscheduled visits:

- (1) If no measurement is available within a visit window, the assessment will be considered missing for the visit;
- (2) If there is more than one measurement available within the same visit window, use the following rules:

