z All concomitant medications are collected through the Safety Follow-up Visit for all subjects. For subjects who prematurely discontinue study drug treatment and are followed for certain efficacy assessments after the ETT Visit (see Section 8.1.6 of Clinical Study Protocol), concomitant antibiotic therapy for ‘sinopulmonary signs/symptoms’ are collected through the Week 24 Visit, as described in Section 11.6.4.5.1 of Clinical Study Protocol.

 
• Labs                             
 
○ Coagulation
 
○ Urinalysis
 
 
 
	1-Baseline	Baseline	1	[screening visit, pre-dose Day 1]
	1 - Week 8	Week 8	57	[1*, 71]
	1 - Week 12 (Safety Evaluation Visit)	Safety Follow-up Visit	NA	Use the nominal visit name
	2-Baseline	Baseline	1	[end of TE period for first period +1 , pre-dose Week 17]
	2 - Week 24	Week 8	57	[1*, 71]
	ETT		NA	Follow the individual visit window to be mapped to individual visits
	2 - Safety Follow-up Visit	Safety Follow-up Visit	NA	Use the nominal visit name

 
• Labs                             
 
○ Vitamin levels
 
○ Lipid panel
 
 
 
	1-Baseline	Baseline	1	[screening visit, pre-dose Day 1]
	1 - Week 8	Week 8	57	[1*, 71]
	2-Baseline	Baseline	1	[end of TE period for first period +1 , pre-dose Week 17]
	2 - Week 24	Week 8	57	[1*, 71]
	ETT		NA	Follow the individual visit window to be mapped to individual visits

 
• Spirometry
 
• Standard 12-lead ECG
 
	1-Baseline	Baseline	1	[screening visit, pre-dose Day 1]
	1 – Day 1 Predose and Postdose	Day 1	1	Nominal
	1 – Day 15 Predose and Postdose	Day 15	15	Nominal
		Day 15	15	[1*, 15] if no nominal Day 15
	1 – Week 4	Week 4	29	[Nominal Day 15+1, 43] if there is nominal Day 15; [16, 43] otherwise.
	1 – Week 8	Week 8	57	[44, 71]
	1 - Week 12 (Safety Evaluation Visit)	Safety Follow-up Visit	NA	Use the nominal visit name †
	2 - Baseline	Baseline	1	[end of TE period for first period +1 , pre-dose Week 17]
	2 – Week 17 Predose and Postdose	Day 1	1	Nominal
	2 – Week 18 Predose and Postdose	Day 15	15	Nominal
		Day 15	15	[1*, 15] if no nominal Week 18
	2 – Week 20	Week 4	29	[Nominal Week 18+1, 43] if there is nominal Week 18; [16, 43] otherwise.
	2 – Week 24	Week 8	57	[44, 71]
	ETT		NA	Follow the individual visit window to be mapped to individual visits

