	2 - Safety Follow-up Visit	Safety Follow-up Visit	NA	Use the nominal visit name †

\* only include day 1 post-dose measurements in each period

† for safety assessments use nominal visit and for efficacy assessments use nominal visit if visit day is greater than the upper boundary of the visit window for Week 8 (period 1) or Week 24 (period 2)

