## Note:

1. For spirometry and ECG data on Day 1 and Day 15 of each treatment period, no visit windowing rule shall be applied. Instead, nominal visit will be used.
2. On Day 1 of period 1, the pre-dose ECG measurements are collected as triplicates. The average of pre-dose triplicates will be used as baseline. Only the pre-dose assessments of the triplicate will be used for the baseline. If all the measurements for triplicates are missing or post-dose, the last non-missing pre-dose assessment will be used as the baseline.
3. For all efficacy parameters, if there are multiple measurements within a visit window, the record at the scheduled visit will be used.
  - If there are no measurements at the scheduled visit, then the record closest to the target day will be used
  - If there are multiple records with the same distance to the target day, the latest record will be used.
  - Assessments at early treatment termination (ETT) visit will follow the windowing rules for regular visits up to Week 24.
  - A safety follow-up visit (SFUV) assessment will follow the windowing rules for regular visits if it falls within the upper boundary of the visit window for Week 8 (period 1) or Week 24 (period 2), or remain as SFUV otherwise.
4. For all safety parameters:
  - If there are multiple measurements within a visit window, then the record closest to the target day will be used
  - If there are multiple records with the same distance to the target day, the latest record will be used.
5. Spirometry, BMI, Weight and Height will follow the efficacy windowing rules.

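### For spirometry and ECG, the Day 15 fallback windows in SAP Table 10-3 admit Day 1 post-dose records, in conflict with Note 1 and the table's own Day 1 row

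*SAP*

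**What the plan says.** SAP Section 10.2 sets the analysis visit windows in Table 10-3. For spirometry and standard 12-lead ECG it gives:

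- **Day 1.** The row "1 – Day 1 Predose and Postdose" is assigned by nominal visit, as is its Week 17 counterpart in Period 2.
- **Day 15.** A nominal row comes first. A second row then supplies a fallback window: "1*, 15] if no nominal Day 15" in Period 1 and "1*, 15] if no nominal Week 18" in Period 2.
- **The asterisk.** Its footnote reads "only include day 1 post-dose measurements in each period". Day 1 pre-dose records are therefore outside the window and Day 1 post-dose records are inside it.

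Note 1 below the table states: "For spirometry and ECG data on Day 1 and Day 15 of each treatment period, no visit windowing rule shall be applied". It then directs that the nominal visit be used.

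The selection rules are in Notes 3 and 4. Spirometry follows the efficacy rule: "If there are no measurements at the scheduled visit, then the record closest to the target day will be used". ECG follows the safety rule: "If there are multiple measurements within a visit window, then the record closest to the target day will be used". Under both, ties go to the latest record, and neither sets a maximum distance from the target day. SAP Section 8.1 covers the empty window: "If no measurement is available within a visit window, the assessment will be considered missing for the visit".

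**The concern.** When the nominal Day 15 or Week 18 record is absent, Note 1 leaves the visit missing, while the table tries to fill it from a window that reaches back to the first dosing day. The SAP does not say which takes precedence, so two programmers could build different datasets from the same text.

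The table's version is also undesirable in itself. Day 15 is meant to show the state after two weeks of treatment, and a reading taken hours after the first dose does not. The outputs at stake are:

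- the Day 15 ppFEV1 descriptive summaries, absolute and relative (SAP 8.3.1.2 and 8.3.2.4);
- the ECG summaries, QTcF and heart rate plots and by-visit threshold counts (SAP 8.4.3);
- Day 15 post-dose spirometry (SAP 8.4.6) and the by-visit counts of predose decline (SAP 8.5.1);
- any by-visit model that includes Day 15.

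**Working it through.** The plan gives no figure to reproduce; this is a check of rules against each other.

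**Do Day 1 post-dose records exist?** Yes, by design. The schedule of assessments (SAP Table 10-2, footnotes k and m) has ECGs for all subjects at 1.5, 3, 4 and 6 hours after the morning dose at Weeks 1 and 17. It has spirometry at 2 and 4 hours at those visits for subjects under 18 at screening only.

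**What does the table select?** I applied the Day 15 rule in order: nominal record if present; otherwise Days 1 to 15, with Day 1 limited to post-dose; then the record closest to Day 15. I did this once literally, and once reserving scheduled Day 1 records for Day 1.

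| Records available | Literal reading | Scheduled Day 1 records reserved for Day 1 |
|---|---|---|
| A. No Day 15; scheduled Day 1 pre- and post-dose only | Day 1 post-dose, distance 15 − 1 = 14 days | Missing |
| B. No Day 15; Day 1 pre-dose only (adult spirometry) | Missing | Missing |
| C. No Day 15; Day 1 post-dose plus an unscheduled Day 9 record | Day 9, distance 15 − 9 = 6 days | Day 9 |
| D. No Day 15; scheduled Day 1 records plus an unscheduled Day 1 post-dose record | Day 1 post-dose, distance 14 days | Unscheduled Day 1 post-dose, distance 14 days |
| E. Nominal Day 15 present | Nominal record | Nominal record |

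In pattern A all post-dose records tie at 14 days. If latest is judged by clock time, the tie rule takes the 6-hour ECG or the 4-hour spirometry. The fallback does not say whether the substitute fills the pre-dose or the post-dose slot, although the Day 15 row covers both.

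**What does Note 1 give?** Nominal visit only, so Day 15 is missing in A to D, including C, where the Day 9 record would be lost from Day 15.

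**What happens if the fallback starts at Day 2?** A, B and D become missing, C keeps Day 9, and E is unchanged.

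**What happens if the fallback rows are deleted?** With no nominal Day 15, the Week 4 window runs from Day 16 to Day 43. A record on Days 2 to 15 would then have no analysis visit. Yet SAP 8.1 and the ETT row of Table 10-3 require ETT assessments to be mapped through the regular windows.

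**Which endpoints use Day 15?** The primary, key secondary and other secondary efficacy endpoints (SAP 5.1) average Weeks 4 and 8. None uses Day 15.

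**The case against.** The best reply is that Note 1 covers Day 1 as well as Day 15. If Day 1 data are never windowed, the scheduled post-dose readings belong to Day 1, pattern A becomes missing, and a strict reading of the note bars pattern D too. The fallback would then serve only unscheduled or ETT records from the days between. The asterisk also looks generic: the same lower bound appears for coagulation, vitamin and lipid tests, although Protocol 11.7.2 schedules Day 1 bloods before the first dose. It may be no more than a device to keep baseline records out of post-baseline windows.

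This is a plausible account of the intent, and it shows that a workable joint reading exists. It does not settle the text. Nothing says that a record assigned to Day 1 cannot also enter the Day 15 window, and the reading leaves the Day 1 lower bound contradicted rather than explained. Note 1 also denies any windowing for Day 15, so the fallback conflicts with it even for the intervening days.

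Stronger readings are tempting but are not supported:

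- **Everyone who misses Week 2 or Week 18 gets a first-dose value.** Patterns B and C show otherwise.
- **A count of subjects.** Missing 2% to 5% of visits would mean about 4 to 10 of 204 subjects per period (204 × 0.02 = 4.1; 204 × 0.05 = 10.2). That miss rate is assumed, the count supposes no other Day 2 to 15 record, and it cannot be applied to spirometry because the number of subjects under 18 is not given.
- **A size for the dilution.** With the 116-hour VX-661 half-life in Protocol 8.2.2, once-daily dosing and one compartment, exposure is 1 − 2^(−24/116) = 13% of steady state after one dose, against 1 − 2^(−14×24/116) = 87% after 14. That holds for VX-661 only. The same formula with ivacaftor's 12-hour half-life and 12-hourly dosing gives 1 − 2^(−12/12) = 50% after one dose, and placebo periods have no contrast. Exposure is also not effect on FEV1 or QTcF.
- **Harm to a model-based result.** Protocol 12.3.3.1 describes a repeated-measures model using all post-baseline data, but the SAP prevails where methods differ, and the SAP text following the primary analysis is redacted. Whether Day 15 enters a model cannot be seen.

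**Conclusion.** The conflict is real and applies in both periods. As written, Table 10-3 can label a first-dose reading as Day 15, while Note 1 and the Day 1 row point the other way. The mislabelling needs two conditions together: no nominal Day 15 or Week 18 record, and no other record on Days 2 to 15. For spirometry it also needs a post-dose Day 1 record, which outside the under-18 group would have to be unscheduled.

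This is a minor point. It concerns descriptive and by-visit outputs at one visit and has no bearing on the confirmatory tests. Neither the number of affected values nor their effect on the summaries can be established from the documents. The conclusion rests on reading the table and its footnote literally, and on the absence of any statement that Day 1 records are exclusive to Day 1.

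**What to change.** Before database lock, make three small edits in SAP Section 10.2:

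1. In the spirometry and ECG rows, change the lower bound of both fallback windows (no nominal Day 15; no nominal Week 18) from 1* to Day 2.
2. Keep the rows, so that ETT and unscheduled records on Days 2 to 15 still map to Day 15.
3. Reword Note 1 to say that the nominal visit is used when present, that the Day 2 to 15 fallback applies otherwise, and that Day 1 records are never used for Day 15.

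The cost is two table cells and one note. A few Day 15 values that the literal table would have filled become missing, in line with the SAP's default for an empty window. Deleting the fallback rows would also remove the first-dose values, but it would leave genuine Day 2 to 15 records without an analysis visit.

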## Note:

1. For spirometry and ECG data on Day 1 and Day 15 of each treatment period, no visit windowing rule shall be applied. Instead, nominal visit will be used.
2. On Day 1 of period 1, the pre-dose ECG measurements are collected as triplicates. The average of pre-dose triplicates will be used as baseline. Only the pre-dose assessments of the triplicate will be used for the baseline. If all the measurements for triplicates are missing or post-dose, the last non-missing pre-dose assessment will be used as the baseline.
3. For all efficacy parameters, if there are multiple measurements within a visit window, the record at the scheduled visit will be used.
  - If there are no measurements at the scheduled visit, then the record closest to the target day will be used
  - If there are multiple records with the same distance to the target day, the latest record will be used.
  - Assessments at early treatment termination (ETT) visit will follow the windowing rules for regular visits up to Week 24.
  - A safety follow-up visit (SFUV) assessment will follow the windowing rules for regular visits if it falls within the upper boundary of the visit window for Week 8 (period 1) or Week 24 (period 2), or remain as SFUV otherwise.
4. For all safety parameters:
  - If there are multiple measurements within a visit window, then the record closest to the target day will be used
  - If there are multiple records with the same distance to the target day, the latest record will be used.
5. Spirometry, BMI, Weight and Height will follow the efficacy windowing rules.

### 10.3 Coefficients for Hankinson and Wang Methods for Calculating Predicted Spirometry Parameters

Percent predicted FEV1 is the ratio of FEV1 (L) to the predicted FEV1 (L), expressed as a percentage. The predicted FEV1 (L) will be calculated using the Hankinson and Wang standards.

The Hankinson standard will be applied to male subjects 18 years and older and female subjects 16 years and older; the Wang standard will be applied to male subjects 6 to 17 years and female subjects 6 to 15 years of age. During the study, the subjects who have a birthday that would move them from Wang to Hankinson will use the Wang standard before that birthday and the Hankinson standard at or after that birthday.

Hankinson Normal Values (HNVs) will be calculated for FEV1, forced vital capacity (FVC), forced expiratory flow mid expiratory phase (FEF25-75%), and FEV1/FVC% using the Hankinson equation:

$$\text{Predicted lung function parameter} = b_0 + b_1 \times \text{age} + b_2 \times \text{age}^2 + b_3 \times \text{height}^2$$

In the equation, height is given in centimeters, age is given in years, and the coefficients b0, b1, b2, and b3 are determined based on subject's sex, race, and age group as shown in [Table 10-4](#).

Wang Normal Values (WNVs) will be calculated for FEV1, FVC, FEF25-75%, and FEV1/FVC using the Wang equation:

$$\ln(\text{Predicted lung function parameter}) = \alpha + \beta \ln(\text{height})$$

Wang Normal Values (WNVs) will be calculated for FEV1, FVC, FEF25-75%, and FEV1/FVC using the Wang equation. In the equation, height is given in meters, and the coefficients α and β are determined based on subject's sex, race, and age as shown in [Table 10-5](#) and [Table 10-6](#).

If either height or age is missing, and the spirometry measurement is non-missing, the last non-missing value of height and age will be used in the calculation of predicted values.

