8.2.3 Rationale for Study Population

The study population will be subjects with CF who are 12 years of age and older and are heterozygous for the *F508del-CFTR* mutation and with a second *CFTR* mutation predicted to have residual function. Based on the results from Study 101 (Section 8.2.1), subjects with the *F508del-CFTR* mutation on only 1 allele may respond to VX-661/ivacaftor treatment when the second allele is also responsive to potentiator modulation. The inclusion of subjects with CF who are 12 to 17 years of age is justified based on severity of disease and allometric scaling. The overall disease status for the adolescent and adult populations to be enrolled in this study is anticipated to be similar based on the identical enrollment criteria, particularly the FEV₁ (i.e., FEV₁ ≥40% and ≤90% of predicted normal for age, sex, and height at screening) and the requirement for clinical stability. Additionally, the expected maturity of the cytochrome P450 (CYP) enzymes in adolescents supports their inclusion. The dose regimen of ivacaftor planned for this study (150 mg q12h) is the current labeled dose regimen for patients with CF with gating mutations who are aged 6 years and older. Based on the historical data from the ivacaftor Phase 3 program and the US CF Foundation Registry on weight as a function of age in patients with CF, weights in the adolescent population are expected to be only slightly lower than those of the adult CF population.

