11.6.3 Cystic Fibrosis Questionnaire-Revised

Subjects will be asked to complete the CFQ-R in their native language.^{34,49} The CFQ-R will be completed before the start of any other assessments, as noted in [Table 3-1](#) and [Table 3-2](#). Subjects who are 12 and 13 years of age at Day 1 will complete the CFQ-R Child version themselves, and their parents/caregivers will complete the CFQ-R Parent version, at all visits, regardless of whether the subject subsequently turns 14 years of age during the study. Subjects 14 years of age and older at Day 1 will complete the Adolescent/Adult version of the questionnaire themselves at all visits. The questionnaires provide information about demographics; general quality of life, school, work, or daily activities; and symptom difficulties (pertaining to CF). Copies of the CFQ-R used in this study will be provided in the Study Reference Manual. Validated translations^{35,36} of the CFQ-R, if available, will be provided for participating centers in non-English-speaking countries.

[REDACTED]

- █ [REDACTED]
- █ [REDACTED]
- █ [REDACTED]
- █ [REDACTED]
- █ [REDACTED]
- █ [REDACTED]
- █ [REDACTED]
- █ [REDACTED]
- █ [REDACTED]

[REDACTED]

[REDACTED]

[REDACTED]

[REDACTED]

[REDACTED]

█ [REDACTED]

█ [REDACTED]

█ [REDACTED]

█ [REDACTED]

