## 6.2 Sample Size and Power

The primary efficacy endpoint is the absolute change in ppFEV1 from study baseline to the average of the Week 4 and Week 8 measurements in each Treatment Period.

The null hypotheses to be tested are that the mean absolute change from study baseline in ppFEV1 to the average of the Week 4 and Week 8 measurements is the same for (i) TEZ/IVA and placebo; and (ii) IVA monotherapy and placebo.

Assuming a standard deviation (SD) of 7 percentage points, 30 subjects per sequence are needed to have at least 90% power to detect a 3 percentage point treatment difference between TEZ/IVA and placebo when the mean values of the primary endpoint are being compared. A 2-sided significance level of 0.05 was used in the sample size calculations. Accounting for the testing strategy, the proposed sample size will yield approximately an 85% chance of observing a statistically significant difference between IVA monotherapy and placebo for the primary endpoint, under the assumption that IVA monotherapy is also 3 percentage points better than placebo (refer to Section 8.3.2.3 for a detailed description of the testing strategy). The sample size estimate was based on 10,000 simulation runs with an incomplete block design assuming no dropouts. In the simulation, the correlation between responses to the 2 treatments within a subject was assumed to be zero. After adjusting for an assumed dropout rate of 10%, the sample size was increased to 34 subjects per sequence (204 total subjects).

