**Table 10-4 HNVs Equation Coefficients by Sex, Race, and Age**

Parameter	Sex	Race	Age		b 0	b 1	b 2	b 3
			(years)					
HNV FEV1	Male	Caucasian	<20		-0.7453	-0.04106	0.004477	0.00014098
			≥20		0.5536	-0.01303	-0.000172	0.00014098
		African American	<20		-0.7048	-0.05711	0.004316	0.00013194
			≥20		0.3411	-0.02309		0.00013194
		Mexican American	<20		-0.8218	-0.04248	0.004291	0.00015104
			≥20		0.6306	-0.02928		0.00015104
	Female	Caucasian	<18		-0.8710	0.06537		0.00011496
			≥18		0.4333	-0.00361	-0.000194	0.00011496
		African American	<18		-0.9630	0.05799		0.00010846
			≥18		0.3433	-0.01283	-0.000097	0.00010846
		Mexican American	<18		-0.9641	0.06490		0.00012154
			≥18		0.4529	-0.01178	-0.000113	0.00012154
HNV FVC	Male	Caucasian	<20		-0.2584	-0.20415	0.010133	0.00018642
			≥20		-0.1933	0.00064	-0.000269	0.00018642
		African American	<20		-0.4971	-0.15497	0.007701	0.00016643
			≥20		-0.1517	-0.01821		0.00016643
		Mexican American	<20		-0.7571	-0.09520	0.006619	0.00017823
			≥20		0.2376	-0.00891	-0.000182	0.00017823
	Female	Caucasian	<18		-1.2082	0.05916		0.00014815
			≥18		-0.3560	0.01870	-0.000382	0.00014815
		African American	<18		-0.6166	-0.04687	0.003602	0.00013606
			≥18		-0.3039	0.00536	-0.000265	0.00013606
		Mexican American	<18		-1.2507	0.07501		0.00014246
			≥18		0.1210	0.00307	-0.000237	0.00014246
HNV FEF25-75%	Male	Caucasian	<20		-1.0863	0.13939		0.00010345
			≥20		2.7006	-0.04995		0.00010345
		African American	<20		-1.1627	0.12314		0.00010461
			≥20		2.1477	-0.04238		0.00010461
		Mexican American	<20		-1.3592	0.10529		0.00014473
			≥20		1.7503	-0.05018		0.00014473
	Female	Caucasian	<18		-2.5284	0.52490	-0.015309	0.00006982
			≥18		2.3670	-0.01904	-0.000200	0.00006982
		African American	<18		-2.5379	0.43755	-0.012154	0.00008572
			≥18		2.0828	-0.03793		0.00008572
		Mexican American	<18		-2.1825	0.42451	-0.012415	0.00009610
			≥18		1.7456	-0.01195	-0.000291	0.00009610
HNV FEV1/FVC%	Male	Caucasian			88.066	-0.2066		
		African American			89.239	-0.1828		
		Mexican American			90.024	-0.2186		
	Female	Caucasian			90.809	-0.2125		
		African American			91.655	-0.2039		
		Mexican American			92.360	-0.2248		

Source: Reference 1 (Tables 4, 5 and 6)

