**Table 10-5 WNVs Equation Coefficients by Sex and Age in White Boys and Girls**

Sex	Age	FEV 1		FVC		FEF 25-75%		FEV 1 /FVC	
		$\alpha$	$\beta$	$\alpha$	$\beta$	$\alpha$	$\beta$	$\alpha$	$\beta$
Male	6	-0.109	2.252	-0.024	2.470			-0.078	-0.248
	7	-0.104	2.270	-0.018	2.489			-0.086	-0.220
	8	-0.089	2.257	0.005	2.443	0.264	1.505	-0.091	-0.199
	9	-0.063	2.197	0.017	2.426	0.308	1.443	-0.086	-0.206
	10	-0.057	2.212	0.030	2.407	0.290	1.557	-0.081	-0.209
	11	-0.093	2.324	0.009	2.468	0.242	1.738	-0.101	-0.147
	12	-0.161	2.512	-0.061	2.649	0.165	1.982	-0.101	-0.133
	13	-0.292	2.843	-0.175	2.924	0.007	2.396	-0.116	-0.085
	14	-0.329	2.983	-0.219	3.060	0.014	2.483	-0.106	-0.087
	15	-0.141	2.709	-0.079	2.859	0.241	2.163	-0.060	-0.155
	16	0.062	2.409	0.104	2.591	0.503	1.764	-0.045	-0.178
17	0.262	2.099	0.253	2.374	0.762	1.368	0.008	-0.272	
Female	6	-0.109	1.949	-0.013	2.007			-0.097	-0.055
	7	-0.144	2.243	-0.062	2.385			-0.084	-0.132
	8	-0.137	2.239	-0.055	2.381	0.247	1.668	-0.079	-0.152
	9	-0.123	2.222	-0.039	2.351	0.254	1.710	-0.084	-0.128
	10	-0.161	2.364	-0.068	2.458	0.195	1.933	-0.092	-0.097
	11	-0.223	2.558	-0.120	2.617	0.161	2.091	-0.102	-0.061
	12	-0.264	2.709	-0.174	2.776	0.185	2.120	-0.090	-0.067
	13	-0.153	2.535	-0.061	2.576	0.294	1.976	-0.093	-0.040
	14	0.046	2.178	0.139	2.208	0.450	1.711	-0.096	-0.026
	15	0.148	2.008	0.210	2.099	0.581	1.486	-0.062	-0.093

Source: Reference 2 (Tables 2 and 3)

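### Does changing the lung-function reference equation on a birthday during the study distort the primary endpoint?

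*SAP*

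**What the plan says.** SAP 10.3 sets the age bands: "The Hankinson standard will be applied to male subjects 18 years and older and female subjects 16 years and older". Below those ages the Wang equation applies. A subject who reaches the threshold during the study "will use the Wang standard before that birthday and the Hankinson standard at or after that birthday". Protocol 11.6.1 gives the same bands for subjects aged 12 and over but has no rule for birthdays on study.

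The primary endpoint (SAP 8.3.1.1) is the absolute change in percent predicted FEV1 from study baseline to the average of Weeks 4 and 8 in each period. The primary model (SAP 8.3.1.2) has treatment, period and baseline percent predicted FEV1 as fixed effects. SAP 6.2 sizes the trial to "detect a 3 percentage point treatment difference between TEZ/IVA and placebo when the mean values of the primary endpoint are being compared".

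For the key secondary endpoint, Protocol 11.6.3 fixes the child version of the questionnaire by age at Day 1, "regardless of whether the subject subsequently turns 14 years of age during the study".

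**The concern.** The two equations do not meet at the threshold. For a White subject with unchanged FEV1 and height, the predicted value rises on the birthday, so percent predicted FEV1 falls. The fall enters change from study baseline and falls mostly on later visits. Because a birthday belongs to one subject, neither the period term nor the baseline covariate removes it for that subject. If it falls inside a treatment period, it also uses up part of the 10-point margin for the listing of declines in SAP 8.5.1.

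A step of 4.7 points in a trial sized for 3 suggests that the measurement rule could mask or mimic a treatment effect. The plan also takes the opposite approach for the questionnaire, so the rule looks like an oversight that one sentence would cure.

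**Working it through.** **The plan's own figure first.** Inputs from SAP 6.2: SD 7, difference 3, two-sided 0.05, 30 per sequence, within-subject correlation 0. Each treatment appears in 4 of the 6 sequences, so there are 4 × 30 = 120 observations per treatment.

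- SE = 7 × √(2/120) = 0.904, which gives power 0.913. The plan says at least 90%.
- Probability that both comparisons succeed (test statistics correlated 0.5): 0.853. The plan says about 85%.
- 30/0.9 = 33.3, rounded up to 34 per sequence, or 204 in all. There are then 4 × 34 = 136 observations per treatment, and SE = 7 × √(2/136) = 0.849.

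**Step for one subject.** Coefficients are from SAP Tables 10-4 and 10-5. Entry values are "≥40% and ≤90% of predicted normal for age, sex, and height at screening". Heights are assumed.

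- Wang: exp(α + β ln height in m). White girl aged 15: α 0.148, β 2.008. White boy aged 17: α 0.262, β 2.099.
- Hankinson: b0 + b1·age + b2·age² + b3·height² in cm. White female under 18: −0.8710 + 0.06537·age + 0.00011496·h². White male under 20: −0.7453 − 0.04106·age + 0.004477·age² + 0.00014098·h².
- Step = ppFEV1 × (Wang/Hankinson − 1).

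| White subject at 90% predicted | Wang (15 or 17) | Hankinson (16 or 18) | Step |
|---|---|---|---|
| Girl, 150 cm | 2.617 L | 2.762 L | −4.7 |
| Girl, 160 cm | 2.980 L | 3.118 L | −4.0 |
| Boy, 160 cm | 3.485 L | 3.575 L | −2.3 |
| Boy, 180 cm | 4.463 L | 4.534 L | −1.4 |

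The 4.7 therefore reproduces, but it is not a ceiling: a White girl of 145 cm at 90% falls 5.1, and a Black girl of 145 cm at 90% rises 1.1. If the birthday falls between Week 4 and Week 8, that period's endpoint moves by half the step.

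**How much is the change of equation?** The table also changes age by a year. At equal age:

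- White boy, 160 cm, aged 17: Hankinson gives 3.460 L, below Wang's 3.485 L, so 90% would rise by 0.7. The boys' fall comes from the extra year.
- White girl, 160 cm, aged 15: Hankinson gives 3.053 L, so 90 × (2.980/3.053 − 1) = −2.2 of the −4.0. About half is the equation.

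**Birthdays inside the Wang table.** White boy, 160 cm, turning 16: 3.103 L to 3.301 L, or −5.4 points at 90%. White girl, 150 cm, turning 14: 2.399 L to 2.532 L, or −4.8. These steps are as large as those at the switch, and they occur at more ages.

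**Effect on the trial result.**

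- Crossers: 204 × adolescent share ÷ 6 (one year of age out of 12 to 17) × 168/365.25 (Day 1 to Day 169). Shares of 10% and 30% give 1.6 and 4.7 subjects.
- Worst imbalance: five crossers with the full fall all on one treatment move its mean by 5 × 4.7/136 = 0.17 points.
- Simulation (20,000 runs, 204 subjects, SD 7, correlation 0, treatment and period in the model, a 4.7-point fall in every crosser, birthdays uniform): with no crossers, mean difference 3.00, SE 0.849, power 94.1%. With 2, 5, 10 or 16 crossers, mean 3.00, SE 0.850 to 0.853, power 93.9% to 94.1%. These differences are within simulation error.

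**Would one equation throughout help?** Suppose crossers had Hankinson at every visit with actual age in completed years. At 90% and 160 cm, the White girl's step shrinks from −4.0 to −1.9, but the White boy's grows from −2.3 to −2.9. The steps inside Wang stay, and the rule departs from the age bands in Protocol 11.6.1.

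**The case for a change.** The best case for a change is that the inconsistency is real, can be checked from the SAP's own tables, enters the primary endpoint and is cheap to avoid. For White girls about half the step is purely the change of formula. Holding each subject's study-baseline equation and age at all visits would make the step zero when height is unchanged, and would remove the Wang birthday steps too. The questionnaire rule shows that the authors saw the principle. A crossing inside a period could also push a subject over the 10-point line.

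The description stands; the consequence does not. Holding equation and age fixed would tidy a few subjects' values but change no trial result by a visible amount. Percent predicted FEV1 is by definition referenced to current age and height, so the comparison with a fixed questionnaire version is loose. The listing in SAP 8.5.1 shows FEV1 in litres beside percent predicted FEV1, so a reader can see a fall that has no counterpart in litres. Section 10.3 also does not say whether age is decimal or in completed years; analysts must settle this in programming, and the choice applies equally to all treatments. Text after SAP 8.3.1.2 is redacted, so a sensitivity analysis on this point cannot be called absent.

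**Conclusion.** No change to the plan is needed. The rule can shift an affected subject's percent predicted FEV1 by about 2 to 5 points for White girls and 1 to 2.3 for White boys across the heights and entry values checked. Such shifts come from yearly age-referenced prediction as much as from the switch of equation. They affect few subjects and are unrelated to randomised sequence. Each pair of treatments is given in both orders, and period is in the model. What remains is slight noise: at most about 0.17 points on a treatment mean with five crossers, against a 3-point difference between means and an SE of 0.849.

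This rests on assumptions the documents do not supply: adolescents are 10% to 30% of subjects, ages and birthdays are evenly spread, Wang uses completed years, and FEV1 and height are unchanged across the birthday. It also uses the plan's SD of 7 and zero correlation. The conclusion is not sensitive to the adolescent share: 16 crossers, about the number expected if every subject were an adolescent (204 ÷ 6 × 168/365.25 = 15.6), still left power at about 94%.
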